## 9. INCLUSION AND EXCLUSION CRITERIA

### 9.1. Inclusion Criteria:

- Adults ( $\geq 18$  years).
- Spanish or English speaker.
- Previous documentation within the past 24 months of hypertension or high blood pressure (SBP 130-179 mmHg or DBP 80-109 mmHg) from general practitioner, pharmacist or health care professional (e.g., medical assistant, physician or nurse).

And either:

1) Untreated (automated) clinic SBP 140-179 or DBP 90-109 mmHg in the last 12 weeks.

Or

2) Monotherapy with clinic SBP 130-159 or DBP 85-99 mmHg in the last 12 weeks.

A SBP or DBP level higher than these thresholds would lead to ineligibility. However, if an individual were eligible based on an in-range SBP or DBP level (i.e., isolated systolic

hypertension or isolated diastolic hypertension), then a lower corresponding DBP or SBP would not lead to exclusion.

And 1 of the following:

- Treatment naïve
- Currently not on treatment (not take in last 4 weeks)
- Currently taking 1 BP lowering drug (ACE, ARB, CCB, thiazide- or thiazide-like diuretic, BB, MRA, alpha blocker) at any dose

The blood pressure inclusion criteria align more closely with the QUARTET trial. The table shows the range of automated office (clinic) blood pressures for inclusion, as well as a comparison with the QUARTET study in Australia. Safety data from QUARTET (Australia) were published in August 2021. Among 591 participants followed for 12 weeks, there were 7 (3%) SAEs in the intervention group (one each of positional vertigo, shortness of breath, non-cardiac chest pain, tonic clonic seizure, fracture of ankle, cholecystitis, and migraine) and 3 (1%) SAEs in the control group (one each of non-cardiac chest pain, pneumonia, and myocardial infarction). There were 12 (4.0%) treatment withdrawals for any event in the intervention group, versus seven (2.4%) in the control group.

	SBP lower limit, mmHg	SBP upper limit, mmHg	DBP lower limit, mmHg	DBP upper limit, mmHg
Automated office (clinic) measurement within the last 12 weeks, untreated	140	179	90	109
Automated office (clinic) measurement within the last 12 weeks, on monotherapy	130	159	85	99
Research grade blood pressure measurement in QUARTET Australia	No limit	No limit	No limit	No limit
Research grade blood pressure measurement (baseline mean)	115	None	60	None

A SBP or DBP level higher than these thresholds would lead to ineligibility. However, if an individual were eligible based on an in-range SBP or DBP level (i.e., isolated systolic hypertension or isolated diastolic hypertension), then a lower DBP or SBP would not lead to exclusion.

If either or both mean research grade blood pressures were lower than the listed SBP and DBP thresholds, then the participant would not be eligible.

## **9.2. Exclusion criteria:**

- Known contraindication to candesartan, amlodipine, indapamide or bisoprolol.
- Previous diagnosis of coronary artery disease, stroke, or heart failure.
- Presence of significant proteinuria (based on 3+ proteinuria via spot urinalysis or >300 mg/dL of proteinuria based on random urinary albumin-to-creatinine ratio testing of 300 mg/g)
- Evidence of secondary cause of hypertension e.g., renal artery stenosis; significant renal impairment (eGFR <50 ml/min/1.73 m^2), raised serum potassium (above lab normal limit of 5.5 mEq/L).
- Women who are pregnant, breast feeding or of childbearing potential and are not using and do not plan to continue using medically acceptable form of contraception throughout the study (pharmacological or barrier methods).
- Concomitant illness, physical impairment or mental condition which in the opinion of the study team / primary care physician could interfere with the conduct of the study including outcome assessments.
- Participation in a concurrent interventional medical investigation or pharmacologic clinical trial. Patients in observational, natural history or epidemiological studies not involving an intervention are eligible.
- Participant's responsible primary care or other responsible physician believes it is not appropriate for participant to switch current monotherapy.
- Inability or unwillingness to provide written informed consent.
- Unable to complete study procedures.

This study will not include any of the following special populations: a) adults unable to consent; b) individuals who are not yet adults (minors): i.e. infants, children, or teenagers; c) pregnant women; or d) prisoners or other detained individuals.

We will identify a list of potentially eligible participants at the participating site(s) through the Epic-based health information technology system at Access Community Health Network. After obtaining a list of potential participants, the study staff will review these potential participants' charts in the EHR, ensure permission from the patients' treating physicians to contact for potential participation in the QUARTET USA study, and call or electronically message these potential participants to determine interest in an initial telephone screen. Electronic messages will be sent through MyChart. If patients express interest, then the study coordinator will schedule a two-day screening visit. During the screening visit, the coordinator will obtain informed consent and conduct baseline assessments with the study nurse to determine eligibility status. Potentially eligible participants will be fitted for an ABPM and asked to wear it for 24 hours and return to clinic. The study coordinator and nurse will conduct a final assessment on eligibility based on the 24-hour ABPM and any other outstanding assessments / results upon the participant's return to clinic. Eligible participants will then be randomized via the randomization module in REDCap. The randomization module will return a study drug kit number. This will preserve the blinding of treatment allocation, since only the study statistician (or representative as a backup) will have access to the master list of drug kit numbers and corresponding treatment codes.

## 10. PARTICIPANT POPULATION(S)

Accrual Number:	Category/Group: (Adults/Children Special/Vulnerable Populations)	Consented: Maximum Number to be Consented or Reviewed/Collected/Screened	Enrolled: Number to Complete the Study or Needed to Address the Research Question
Local	Adults	No Limit	87
Study-wide	Adults	No Limit	87
Total:	Adults	No Limit	87

## 11. RECRUITMENT METHODS

Participants will be recruited from two of the community clinics within Access Community Health Network using its Epic-based health information technology system. This system allows for rapid electronic identification of eligible participants based on routinely collected clinical data as well as direct communication with their clinicians to seek their permission to contact potential participants. This methodology has been used in numerous studies between Northwestern investigators and ACCESS for successful recruitment. Participants may be contacted for screening either by phone or through electronic messaging, through MyChart. After initial contact by phone or electronic messaging, participants may also be contacted via text for appointment scheduling and reminders and retention.

In the event of lagging recruitment or lack of diversity in study population to reach our targets, we plan to open up recruitment and enrollment efforts to additional Access Community Health Network site(s). If this occurs, then we will submit a protocol amendment and seek IRB approval prior to initiating study procedures at any additional sites.

## 12. COMPENSATION FOR PARTICIPATION IN RESEARCH ACTIVITIES

Study participants will be paid according to the following schedule via cash (\$30 per study visit and reimbursement for transportation costs with CTA or PACE cards (\$5 per round trip). The maximal amount to be paid for participating in this study is \$115.

	Screening and Randomization		6-Week Follow-up Visit	12-week Follow-up Visit		
	Payment Schedule	Visit 1	Visit 2	Visit 3	Visit 4	Visit 5
Incentive (cash)	\$15 if ineligible to continue		\$30	\$30	-	\$30

PACE, CTA, Lyft or equivalent	\$5	\$5	\$5	\$5	\$5
Automated home blood pressure monitor		X			

Some participants may be ineligible after completing components of the screening and randomization visits. If the participant has attended a single visit and has been determined ineligible, they will be compensated \$15. If the participant has attended two visits and has been determined ineligible or eligible, they will be compensated \$30.

### **13. WITHDRAWAL OF PARTICIPANTS**

If a participant is withdrawn or decides to withdraw from the study, then attempts will be made to conduct a close-out visit, which will include the assessments planned for the 12-week visit. Data that have been already collected will not be removed from the study database unless explicitly requested by the participant.

If the study physician / medical monitor / DSMB deems it unsafe for any participant to continue study drug or any study procedures, then he / she may withdraw the study participant without his / her consent. If a study participant experiences an AE requiring discontinuation of study drug, then we will collect any remaining study drug and refrain from any additional dispensation for that participant. We will continue to follow the participant and collect all required follow-up data per the study visit schedule. If a participant is incarcerated, becomes terminally ill, or experiences any other circumstance that would make continued involvement in the study unfeasible or unethical, then the study team may withdraw the participant without his / her consent. In all cases, any data already collected will not be removed from the study database and may still be used in analyses unless explicitly requested by the participant.

### **14. RISKS TO PARTICIPANTS**

- The risks of taking a blood sample include pain, a bruise at the point where the blood is taken, redness and swelling of the vein, infection, and a rare risk of fainting.
- The ECG procedure may cause some redness or itching on the skin where the leads are placed.
- If participants are randomized to the control arm, then they will be taking candesartan, an FDA-approved drug for the treatment of hypertension (high blood pressure).
- If participants are randomized to the active intervention arm, then they will be taking the four-drug combination pill, which includes ultra-low doses of candesartan, amlodipine, indapamide, and bisoprolol. These drugs are each approved by the FDA for treatment of hypertension, but a combination pill of these medications at these lower doses has not been approved to date. The known side effects of each of these medicines are shown

below. These side effects typically go away after stopping the medication. If any of these side effects occur while a participant is in the trial, then they will be reported as AEs.

Very common:	More than 1 out of 10 people have reported this side effect
Common:	From 1 to 10 out of 100 people reported this side effect
Uncommon:	From 1 to 10 out of 1,000 people have reported this side effect
Rare:	From 1 to 10 out of 10,000 people have reported this side effect
Very rare:	Less than 1 in 10,000 people have reported this side effect

The frequency of side effects is based on standard doses, and an important hypothesis of this study is that quarter doses, even in combination, will be better tolerated than a standard dose.

Reported Side Effects	Amlodipine	Bisoprolol	Candesartan	Indapamide
Allergic reactions like skin rash, itching or hives, or swelling of the face, lips, or tongue	Uncommon	Rare	Rare	Common
Anxiety		Uncommon		Uncommon
Blurred vision or changes in vision or hearing	Uncommon			Common
Breathing problems	Uncommon	Uncommon	Uncommon	
Change in sex drive or performance		Uncommon	Uncommon	
Chest pain	Rare	Common	Common	
Cold, tingling or numb hands or feet		Common		
Confusion		Uncommon		
Cough			Uncommon	
Depression		Uncommon		
Diarrhea		Common		Common
Dry mouth	Uncommon			Rare
Dry or burning eyes		Uncommon		
Facial flushing	Uncommon			

Feeling faint or lightheaded or falling			Very common	
Headache		Common	Common	Common
Infection or flu-like symptoms				Common
Irregular or fast heartbeat	Uncommon		Uncommon	Common
Irregular or slow heartbeat		Very common		Common
Loss of appetite				Common
Muscle aches and pains		Common		Common
Muscle cramps or spasms				Common
Nausea, vomiting	Uncommon	Common	Common	Uncommon
Passing less urine			Common	
Redness, blistering, peeling or loosening of the skin, including inside the mouth				Very rare
Stomach gas, pain	Common		Common	
Sweating		Uncommon		
Swelling of hands or feet			Uncommon	
Swelling of legs or ankles	Very common	Uncommon		
Tremors		Uncommon		
Trouble sleeping	Uncommon			
Unusually weak or tired	Uncommon			Common

- In addition to these risks, this research may harm participants in ways that are unknown. These may be a minor inconvenience or may be so severe as to cause death but this is not expected.
- This study involves the use of participants' identifiable, personal health information and there is a chance that a loss of confidentiality could occur. The researchers have procedures in place to lessen the possibility of this happening.
- The study drug may also hurt a pregnancy or fetus in ways that are unknown. These may be a minor inconvenience or may be so severe as to cause death. Participants currently pregnant or nursing will be excluded from this study, and eligibility is contingent on participants' willingness to use acceptable forms for birth control. If participants become pregnant during the course of the study, then they are asked to notify the study team, and the study team will halt study drug administration. The study team will

continue to follow these participants and collect any AE and study-related data through the final study time point.

## **15. POTENTIAL BENEFITS TO PARTICIPANTS**

During this research study, participants will receive blood pressure lowering medication, which may help control their blood pressure during this period.

## **16. DATA MANAGEMENT AND CONFIDENTIALITY**

Paper CRFs will be housed at the study site in a locked, secure location. Only authorized study staff, monitors or auditors will have access to these files. Electronic data will be stored in the eCRFs maintained using the Northwestern University REDCap platform. Thus, only those with an appropriate Northwestern NetID and password will have ability to enter and view study data. Export rights will be restricted to the study statistician only, and data will only be exported when necessary for reporting and quality control purposes to a restricted 'fsmresfiles' location at Northwestern. The randomization list and any blinded material will also only be restricted to the study statistician, with files located on fsmresfiles with restricted access.

To ensure data quality, we will build in field validation(s) and branching logic within the forms, use a first / second pass data entry workflow, and we will use the field comment logs and data resolution workflow module within REDCap. Before obtaining data entry rights in production, study team members must complete a training and pilot test entry of hypothetical data. We will document these training sessions and successful completion of any study data entry practicums.

Further, we will perform centralized monitoring through Data and Status Quality Reports (DSQRs) and REDCap reporting features. The DSQRs will use the REDCap application programming interface (API) functionality to export the study data, and then restructure and summarize the data using statistical software such as R or SAS. The output for these DSQRs will be housed on Northwestern University's secure servers with restricted access to study team members only. The reports will be reviewed and discussed weekly, on average, but once the systems are in place and code generated, the reports may be updated in real-time.

The contents of these reports may continually evolve throughout the course of the study, but they will focus on the following essential study data:

- Baseline information – screening and consent, enrollment, demographics
- Adherence to intervention (pill counts) and protocol adherence
- Primary and secondary response variables
- AEs / SAEs
- Concomitant medications
- Other pre-specified response variables and/or covariates (laboratory data, exploratory outcomes)

For the purposes of these reports, we will only present data in aggregate form (i.e., we will not summarize results by study arm) overall. In addition to these general data summarizations, we plan to employ statistical methods for monitoring clinical trial data. The general strategies include:

- Exploration of:
  - Descriptive statistic summaries overall and by site for essential study data as indicated above.
  - Frequency of outlying values overall and by site.
  - Process measures overall and by site:
    - Screen failure rate
    - Outlier and inlier rates
    - Correlation coefficients of key covariates
    - Deviations and AEs by site
    - Timeliness of data entry
    - Proportion of dropouts / losses to follow-up
- Evaluating important response and safety data univariately and also longitudinal trajectories over time (within the same person).
- Multivariate techniques involving principal components (PC1 vs. PC2) and examining multivariate outliers. For example, we may examine mean for individual center vs. that of all other centers. Plot PCs for p-values for all variables and identify outliers (those outside of the central cloud).
- Tests on randomness – Benford’s law on the distribution of digits.

### 16.1. Sample Size

A target of 87 participants will be randomized (1:1 allocation). The analytic sample size of 77 is anticipated based on 87 participants at randomization and a conservatively estimated 12% dropout rate by the 12-week follow-up time point based on 8% dropout rate observed through September 2021. This sample size is conservatively based on an independent two-sample t-test. The analysis methods, linear mixed models including a fixed baseline value term, will increase precision on intervention effect when controlling for relevant baseline covariates, thereby providing additional power of detecting intervention effect.

The initial, conservative sample size and power calculations based on an independent two-sample t-test suggested 80% power to detect a 5 mmHg difference in SBP between the intervention and comparator arms assuming a two-sided 5% level of significance and a 15 mmHg standard deviation in outcome. At the request of the DSMB, we conducted an interim conditional power analysis, taking into consideration information from both the QUARTET USA trial data as of August 2021 and further the QUARTET (Australia) results. These interim analyses, incorporating information to date, suggested that a recruited sample size of at least 77, and a 12% dropout rate, would provide over 90% conditional power based on a sample of 87 randomized participants.

Previously, the protocol required the 24-hour ambulatory blood pressure assessments, and we thus conducted initial power calculations based on several *a priori* assumptions for this endpoint as follows: Since expected mean 24-hour ambulatory blood pressure may be more precise than office blood pressure (with a standard deviation of 12 mmHg vs. 15 mmHg for office blood pressure), over 95% power was anticipated with the original sample size (N=364) to detect a 5 mmHg difference across arms in this important secondary outcome under the same assumptions as outlined for our primary outcome (office blood pressure). However, subsequent protocol modifications allowed for optional 24-hour ambulatory blood pressure, and this outcome has been modified to become an exploratory outcome.

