8. POWER AND SAMPLE SIZE CONSIDERATIONS

The initial sample size calculations called for a total of 365 participants to be randomized (1:1 allocation). We anticipated an analytic sample size of 292 based on 365 participants at randomization and a 20% dropout rate by the 12-week follow-up time point. We originally based sample size and power calculations conservatively on an independent two-sample t-test. Based on results of interim analyses (refer to Section 10 for details), we updated our recruitment target to 87 participants (1:1 allocation). The analytic sample size of 77 is anticipated based on 87 participants at randomization.

and a conservatively estimated 12% dropout rate by the 12-week follow-up time point based on 8% dropout rate observed through September 2021.

The initial, conservative plan for primary outcome analyses involving an independent two-sample t-test provided an estimated 80% power to detect a 5 mmHg difference in SBP between the intervention and comparator arms assuming a two-sided 5% level of significance and a 15 mmHg standard deviation in outcome. This estimate is based on a 2017 Cochrane systematic review update evaluating the effects of fixed-dose combination therapy and systematic review on quarter dose combination therapy, and a pilot trial of quarter-dose combination therapy [3]. We assumed baseline SBP has a moderate correlation with follow-up SBP ($r \approx 0.50-0.6$); under this assumption, sample size calculations based on ANCOVA has the potential to allow for over 90% power under the same assumptions for remaining parameters.

At the request of the DSMB, we conducted an interim conditional power analysis, taking into consideration information from both the QUARTET USA trial data as of August 2021 and further the QUARTET (Australia) results.¹⁰ These interim analyses, incorporating information to date, suggested that a recruited sample size of at least 77, and a 12% dropout rate, would provide over 90% conditional power based on a sample of 87 randomized participants.

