Previously, the protocol required the 24-hour ambulatory blood pressure assessments, and we thus conducted initial power calculations based on several a priori assumptions for this endpoint as follows: Since expected mean 24-hour ambulatory blood pressure may be more precise than office blood pressure (with a standard deviation of 12 mmHg vs. 15 mmHg for office blood pressure), we estimate over 95% power with the planned sample size to detect a 5 mmHg difference across arms in this important secondary outcome, under the same assumptions as outlined for our primary outcome (office blood pressure). However, subsequent protocol modifications allowed for optional 24-hour ambulatory blood pressure, and this outcome has been modified to become an exploratory outcome.

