10. TIMELINE FOR ANALYSES

As this is a phase II clinical trial, the original analysis plan did not include any formal interim statistical analyses involving hypothesis testing or any pre-specified stopping criteria for efficacy or futility on primary or secondary outcomes. Interim reports to the study team and data and safety monitoring board (DSMB) will consist of process measures such as protocol departures, missing values, missing forms, treatment regimen adherence, etc. and simple descriptive statistics on primary and safety outcomes of interest. In addition, weekly meetings with the study team will utilize central statistical monitoring techniques as a method of quality control and quality assurance for trial data on an ongoing basis. We foresee the DSMB requiring specific data listings or summarizations, but these will be specified at the time of the relevant DSMB meeting(s). At the request of the DSMB, we conducted an interim conditional power analysis, taking into consideration from both the QUARTET USA trial data as of August 2021 and further the QUARTET (Australia) results. These interim analyses, incorporating information to date, resulted in an updated recruitment target (and thus overall sample size goal). These interim analyses also resulted in the ultimate updates to the analytic strategy from an ANCOVA to one involving a mixed modeling approach to make use of both the six- and 12-week follow-up data for all participants. These modifications to the analytic plan resulted in an updated SAP (to version 2.0).

To preserve the integrity of the study, no formal final statistical analyses will occur until the REDCap database has been locked and all queries/discrepancies resolved; the date of database lock will be documented.

References:

1. Harris, P.A., et al., *Research electronic data capture (REDCap): a metadata-driven methodology and workflow process for providing translational research informatics support*. Journal of Biomedical Informatics, 2009. **42**(4): p. 377-381.
2. Scharfstein, D., et al., *Global sensitivity analysis for repeated measures studies with informative dropout: A fully parametric approach*. Statistics in Biopharmaceutical Research, 2014. **6**(4): p. 338-348.
3. Bahiru, E., et al., *Fixed-dose combination therapy for the prevention of atherosclerotic cardiovascular diseases*. Cochrane Database of Systematic Reviews, 2017(3).

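### Protocol 16.1 attributes the current sample size of 87 (77 analysed) to a two-sample t-test, but the only t-test given supports the original 365 (292 analysed), and 87 came from the interim conditional power analysis

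*Protocol*

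**What the plan says.** **Protocol 16.1, first paragraph.** It gives 87 randomised (1:1), 12% dropout and 77 analysed. Directly after that: "This sample size is conservatively based on an independent two-sample t-test". The following sentence says that the mixed model, by adjusting for baseline, increases precision, "thereby providing additional power of detecting intervention effect".

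**Protocol 16.1, second paragraph.** It describes the t-test calculation as initial: 80% power for 5 mmHg, SD 15 mmHg, two-sided 5%. It names no sample size for that calculation. It then reports the conditional power analysis requested by the DSMB and links 87 and 77 to it.

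**SAP section 8.** After giving 365 randomised, 20% dropout and 292 analysed, it says: "We originally based sample size and power calculations conservatively on an independent two-sample t-test". The next sentence is: "Based on results of interim analyses (refer to Section 10 for details), we updated our recruitment target to 87 participants (1:1 allocation"). Further on, the interim result is given as "a recruited sample size of at least 77, and a 12% dropout rate, would provide over 90% conditional power". SAP section 10 also says that the interim analyses produced the new target.

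**24-hour blood pressure.** SAP section 8 says "we estimate over 95% power with the planned sample size to detect a 5 mmHg difference". Protocol 16.1 makes the same claim, but for the original sample size, which it gives as 364.

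**The concern.** In the first paragraph of Protocol 16.1 the only sample size mentioned is 87/77, so the opening words of the quoted sentence have nothing else to refer to. Together with the next sentence, the text presents a t-test at 87/77 as a conservative floor, with the mixed model adding to it. The SAP attaches the same t-test to 365/292 and gives a different origin for 87.

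Two things are at stake. If the sentence is carried into the trial report, the report will misstate how the sample size was set and will pass over the fact that it was reduced after an interim look at trial data. And because the second paragraph of 16.1 quotes 80% t-test power without naming the number analysed, someone reading only the protocol could attach that 80% to 77 participants.

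**Working it through.** **Inputs.** Difference 5 mmHg, SD 15 mmHg, two-sided 5%, 80% power (Protocol 16.1, SAP 8). Original design: 365 randomised, 20% dropout, 292 analysed (SAP 8). Current design: 87 randomised, 12% dropout, 77 analysed (both documents). 24-hour blood pressure: 5 mmHg, SD 12 mmHg (both documents).

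**Numbers analysed.** 365 × 0.80 = 292. 87 × 0.88 = 76.6, which rounds to 77. Both agree with the text.

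**Reproducing the plan's t-test.** By the normal approximation, n per arm = 2 × (1.960 + 0.842)² × (15/5)² = 141.3, so 142 per arm, or 284 in total. With the exact noncentral t, 142 per arm gives 79.9% and 143 per arm gives 80.2%, so 286 analysed are needed. Dividing by 0.80 gives 355 to 358 randomised. This is close to the original 365/292.

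**Power of that test at each size.** The noncentrality is 5 / (15 × √(1/n₁ + 1/n₂)), with n₁ + n₂ − 2 degrees of freedom.

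| Analysed | Standard error (mmHg) | Noncentrality | Power |
|---|---|---|---|
| 292 (146/146) | 1.756 | 2.848 | 81.0% |
| 87 (44/43), no dropout | 3.217 | 1.554 | 33.6% |
| 77 (39/38) | 3.419 | 1.462 | 30.3% |

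With 77 analysed, this test reaches 80% power only for a difference of about 9.7 mmHg. The Australian trial's 6.9 mmHg (Protocol section 2.3) with SD 15 gives 6.9 / 3.419 = 2.018, or about 51%.

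**24-hour blood pressure.** Same formula, SD 12 mmHg.

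| Analysed | Noncentrality | Power |
|---|---|---|
| 364 (182/182) | 3.975 | 97.7% |
| 292 (146/146) | 3.560 | 94.4% |
| 77 (39/38) | 1.828 | 43.8% |

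So by t-test, power of over 95% holds if all 364 are analysed. It narrowly fails at 292 and is far off at 77.

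**The case against.** The strongest reply is that nothing is concealed. The second paragraph of Protocol 16.1 calls the t-test calculation initial and reports the conditional power analysis, and SAP sections 8 and 10 state plainly where 87 came from. The 24-hour paragraph in the SAP likewise opens by saying it describes earlier calculations. No enrolment or analysis decision depends on the misplaced sentence. This stands, and it is why the point is minor.

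A second reply is that the documents do not say which statistic the conditional power analysis used. It may have been a t statistic, in which case a t-test would in some sense lie behind 87. This also stands as a limit: the arithmetic shows only that the t-test the documents specify does not support 87/77. It does not rescue the sentence, because neither document describes such a calculation and the SAP attributes its t-test to the original size.

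A reader might go further and infer that the trial has only 30% power, or that the conditional power of over 90% is wrong. The documents support neither. The 30% is unconditional, at the original assumptions, for a test that is not the planned analysis. The conditional figure depends on interim data, and no interim estimate, information fraction or assumed future effect is given. Nor can power for the baseline-adjusted mixed model be fixed: it would need the correlation between weeks 6 and 12, which is not stated, and a decision on whether the SD of 15 mmHg refers to follow-up pressure or to change from baseline.

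**Conclusion.** The contradiction is real and is one of internal consistency; none of the stated arithmetic is itself wrong. As written, Protocol 16.1 gives the wrong basis for the current sample size. The specified t-test belongs to 365/292, where it gives 81% power, and gives about 30% at 77 analysed. The result rests only on the stated inputs and an even split between arms. The parallel sentence in SAP section 8 on 24-hour blood pressure has the same fault: its figure belongs to the original size, and at 77 analysed the same t-test gives 43.8%. Severity is minor. The figure of over 90% conditional power remains unchecked, not disproved.

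**What to change.** 1. **Protocol 16.1.** Reword to agree with SAP sections 8 and 10: the original sample size (365 randomised, 292 analysed) was based on an independent two-sample t-test, and the target of 87 was set from the interim conditional power analysis. State that the 80% t-test power applies to the original size. State also that the same inputs give about 30% unconditional power with 77 analysed, labelled so that it is not confused with the conditional power.

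2. **SAP section 8, 24-hour blood pressure.** Tie the power of over 95% to the original sample size, as the protocol does, and give the number analysed. By t-test this is 97.7% with all 364 analysed, 94.4% with 292 and 43.8% with 77.

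Do not add power ranges for the baseline-adjusted or pooled models, since they would rest on inputs that the documents do not give.

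The cost is wording in two places, with no change to enrolment or analysis. The one downside is a less favourable stated power.
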